8.2.2. Withdrawal of Consent and Requirements to Re-Enter the Study

Withdrawal of Consent

If the subject decides that it is in his/her best interest to discontinue from the study, he or she may withdraw consent. It is fully understood that all subjects volunteer for the study and that they may withdraw their consent to continue in the study at any time.

A reasonable effort must be made to determine the reason(s) for subject discontinuation. This information and date must be recorded in the appropriate CRF.

Requirements to Re-enter Study after Withdrawal of Consent

Subjects who withdraw consent and want to re-enter the study must confirm that they have not received any investigational product being evaluated for the treatment of diabetes, weight loss, or NASH within 30 days before restarting investigational product or within 5 half-lives of the compound (whichever was longer) before restarting investigational product. Subjects are to be re-consented and new baseline visit procedures must be performed if the interval from the last visit was more than 3 months (+2 weeks) during the first 18 months of the study or more than 6 months prior (+2 weeks) during the remainder of the study.

8.2.3. Lost to Follow-up

If a subject fails to return to the clinic for a study visit, and the Investigator ceases to have contact with the subject, he or she will be withdrawn from the study.

A reasonable effort must be made to contact the subject and determine the reason(s) why a subject fails to return for a study visit or is lost to follow-up, as outlined in the Subject Retention Plan. This information and date of contact must be recorded in the appropriate CRF.

8.2.4. Subject Discontinuation Notification

The Investigator must notify the Medical Monitor by telephone or email as soon as possible if any subject prematurely withdraws from the study. The date when the subject is withdrawn and the reason for discontinuation must be recorded in the CRF. If a subject is “lost to follow-up” (fails to return for a visit), a reasonable effort should be made to contact the subject in order to determine why the subject failed to return. This information must be documented in the CRF. If a subject is withdrawn from the study early (regardless of the cause), all of the EOT/EOS evaluations should be performed at the time of withdrawal, as appropriate (see [Section 9.9.9](#)).

9. TREATMENT OF SUBJECTS

9.1. Investigational Product Treatment Regimen

The term investigational product (provided as part of this clinical study) refers to either OCA or placebo.

Three treatment groups will be evaluated: placebo, OCA 10 mg, and OCA 25 mg. Each dose will be made up of 1 tablet (ie, one placebo tablet, one OCA 10 mg tablet, or one OCA 25 mg tablet).

Investigational product will be taken orally with water, once daily for the duration of the study. Subjects will be instructed to begin dosing on Day 1 and are to take investigational product at approximately the same time each day. Subjects must be instructed to swallow the tablet whole; they must not chew, divide, or crush the tablet.

For subjects participating in the PK portion of the study: All assessments, except for the post-dose collection of blood samples for the subset of subjects participating in the PK assessment, must be completed before administration of investigational product.

Refer to [Section 7.7](#) and [Table 4](#) for adjustments, interruptions, and discontinuation of investigational product per safety criteria.

9.2. Lifestyle Modification Counseling

Despite the serious nature of the disease, there are currently no approved therapies for the treatment of NASH nor accepted standard of care. The therapeutic options for NASH are largely limited to lifestyle modifications, generally encompassing diet and physical activity, and treatment of concurrent conditions such as type 2 diabetes, obesity, hypertension, and dyslipidemia. Lifestyle modifications can be very effective in patients who make significant adjustments to their lifestyle. Therefore, in accordance with the current standard of care, all subjects will receive counseling on lifestyle modification with regard to diet and exercise. Owing to the regional and cultural differences in diet and lifestyle across investigational sites, Investigators will be asked to counsel subjects on ways to maintain a healthy diet and to encourage subjects to engage in an appropriate form of exercise.

9.3. Standard of Care and Concomitant Medications

Concomitant medications will be used at the discretion of the usual care provider (or Investigator if also the usual care provider). Relevant information about all concomitant medications taken before (ie, within 6 months of Day 1) and during the study must be recorded in the source documents and case report form, as well as any dose or dose regimen changes that occur during the study. To the extent possible, concomitant medications should be maintained at a stable dose throughout the study and at a minimum, between Day 1 and Month 18, unless the baseline therapy is no longer considered clinically appropriate by the Investigator. In general, Investigators will be encouraged to follow guidelines for care based upon local and institutional practice patterns and any relevant published practice guidelines.

Exceptions to this general requirement are noted below.

- Subjects providing historical biopsies to determine study eligibility should either not be taking any drugs with potential NASH-modifying properties (specifically, TZDs/glitazones or vitamin E) or should be on a stable dose of these medications for 6 months before Day 1 through Month 18. Changes to these drugs with potential NASH-modifying properties are not permitted, for all subjects, for the first 18 months of the study. Ideally, subjects should generally remain on baseline TZDs/glitazones or vitamin E from Month 18 through the end of the study, unless the baseline therapy is no longer considered clinically appropriate by the Investigator.

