
Additional information regarding the data cutoff date for the Month 18 Interim Analysis population will be defined in the SAP.

Analyses**Efficacy Analyses:**

All efficacy hypothesis testing will be based on the ITT population including only fibrosis stage 2 and stage 3 subjects. Supportive analyses will be conducted using PP population and all fibrosis stages (Full Analysis Population).

The 2-sided alpha allocated to all testing in this single study will be 0.05. The histological endpoints will be tested at the Month 18 Interim Analysis with alpha level of 0.02. The primary clinical outcomes endpoint will be tested with a minimum alpha level of 0.03 and this may be augmented by recycled alpha from the Month 18 interim analysis.

For the Month 18 Interim Analysis, multiplicity adjustment will be implemented to control the type 1 error. Details will be provided in the SAP.

Primary Efficacy Analysis at the Month 18 Interim Analysis:

The primary efficacy analysis for fibrosis improvement at Month 18 will test the following hypotheses using the ITT population (the ITT population for the Month 18 Interim Analysis is not the same as that for the overall study and is defined in the SAP):

- H_{01} : The percentage of subjects with fibrosis improvement by at least 1 stage with no worsening of NASH is equal between placebo and OCA 25 mg.
- H_{11} : The percentage of subjects with fibrosis improvement by at least 1 stage with no worsening of NASH is different between placebo and OCA 25 mg.

The primary efficacy analysis for the resolution of NASH will test the following hypotheses:

- H_{02} : The percentage of subjects with resolution of NASH and no worsening of fibrosis is equal between placebo and OCA 10 mg.
- H_{12} : The percentage of subjects with resolution of NASH and no worsening of fibrosis is different between placebo and OCA 10 mg.

The primary efficacy analyses at the Month 18 Interim Analysis will compare placebo and OCA using a Cochran–Mantel–Haenszel test stratified by the randomization strata (presence of type 2 diabetes at enrollment [yes/no] and use of TZDs/glitazones or vitamin E at baseline [yes/no]). Subjects with missing histology results at Month 18, will be considered non-responders. Post-baseline biopsies at early termination visit (prior to Month 18) will be included in the analysis regardless of the timing of the biopsy.

Secondary Efficacy Analyses at the Month 18 Interim Analysis:**Histology Analysis**

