### **3.4.2. End of Study Analysis Populations**

- The Safety Population will include all randomized subjects who received at least 1 dose of investigational product (OCA or placebo). Treatment assignment will be based on the treatment actually received.
- The Full Efficacy Analysis Population will include all randomized subjects, all fibrosis stages (stages 1, 2 and 3), who received at least 1 dose of investigational product. Treatment assignment will be based on the randomized treatment.
- The Intent-to-Treat (ITT) Population will be a subset of the Full Efficacy Analysis Population, limited to those subjects with fibrosis stage 2 or stage 3. Treatment assignment will be based on the randomized treatment. The ITT Population will be the primary efficacy analysis population. The Per Protocol (PP) Population will include all subjects from the ITT Population who did not have any major protocol deviation ([Section 5.5](#)) that could potentially affect the efficacy conclusions and at least 80% compliance with investigational product ([Section 10.1](#)). Treatment assignment will be based on the randomized treatment.
- The PK Population will include all subjects who received OCA and have at least one confirmed fasted analyzable sample. Subjects must have been fasting for approximately 8 hours before the visit and must not have any major protocol deviations that potentially affect exposure levels. The PK Population will be used for OCA PK.

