**Table 3: Analysis Populations for the Month 18 Interim Analysis and End of Study Analysis**

Population	Fibrosis Stage	Description	
		Month 18 Interim Analysis	End of Study
Safety	1,2 and 3	Randomized subjects who received at least one dose of investigational product by the DCO (IA Cohort)	Randomized subjects who received at least one dose of investigational product.
Full Efficacy Analysis	1,2 and 3	All subjects, randomized by 15 July 2017, all fibrosis stages (stages 1, 2 and 3), who received at least 1 dose of investigational product.	Randomized subjects who received at least one dose of investigational product.
ITT	2 and 3	Subset of Full Efficacy Analysis Population	Subset of Full Efficacy Analysis Population
mITT	2 and 3	Subset of ITT Population which excludes treatment discontinuation (before the Month 18 Visit and without an end of treatment biopsy) between 13 Sep 2017 to 19 Dec 2017 due to withdrawal of consent, lost to follow up and other reasons	Not applicable
Per Protocol	2 and 3	Subset of ITT Population who completed at least 15 months of treatment, had a Month 18/end of treatment biopsy, were on investigational product for at least 30 days just preceding the biopsy, and did not have any major protocol deviation	Subset of ITT Population with no major protocol deviation and at least 80% compliance with investigational product ( Section 10.1 )

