## **5.5. Protocol Deviations**

The Investigator is not permitted to deviate from the protocol in any significant way without notification to the Sponsor (or designee) as described in the protocol.

All eligibility deviations specified in the protocol will be considered major deviations and subjects meeting any of these deviations will not be included in the PP Population. Major on-study protocol deviations that could potentially affect the efficacy or safety conclusions of the study will be identified through programming and identifying selected categories from the list of protocol deviations collected during the study:

- Investigational product dosing, including subjects who receive treatment different from what they were randomized to.
- Taking investigational product after bariatric surgery (gastric bypass)

All major protocol deviations will be summarized and listed by treatment group.

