##### Secondary Endpoints:

[figure not shown]
- Percentage of subjects with no worsening of fibrosis AND no worsening of NASH
- Percentage of subjects with progression to cirrhosis
- Percentage of subjects with improvement of fibrosis by at least 2 stages
- Percentage of subjects with improvement of each key histological feature of NASH by at least 1 point (steatosis, lobular inflammation, and hepatocellular ballooning)
- Percentage of subjects with improvement of NAS by at least 2 points with no worsening of fibrosis
- Percentage of subjects with improvement of fibrosis and resolution of NASH as a composite endpoint and as defined by both endpoints being met in the same subject
- Percentage of subjects with resolution of fibrosis.

[figure not shown]
The analyses will compare placebo and each OCA dose separately (10 mg and 25 mg), using a CMH test stratified by the randomization strata (diabetes at enrollment [yes/no] and use of TZDs or vitamin E at baseline [yes/no]).

These analyses will also be conducted using the mITT, PP and Full Efficacy Analysis Populations.

At the End of Study Analysis, all Month 18 histological endpoints will be analyzed.

[figure not shown]

S

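### SAP 5.5's major on-study deviations omit the prohibited TZD/glitazone and vitamin E changes before Month 18, so these subjects stay in the End of Study Per-Protocol set unless another criterion removes them (minor)

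*Protocol*

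**What the plan says.** Protocol 9.3 describes TZDs/glitazones and vitamin E as potentially NASH-modifying and sets a rule without exceptions: "Changes to these drugs with potential NASH-modifying properties are not permitted, for all subjects, for the first 18 months of the study". From Month 18 on, it asks for stability only as an ideal. Protocol 16.1 defines the PP Population as ITT subjects free of major violations that might affect the efficacy conclusions, and leaves the categories open.

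SAP 5.5 supplies the categories. All eligibility deviations are major. Major on-study deviations "will be identified through programming and identifying selected categories from the list of protocol deviations collected during the study", and two follow: investigational product dosing (including receipt of the wrong treatment), and product taken after bariatric surgery. The section adds that "All major protocol deviations will be summarized and listed by treatment group".

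SAP 3.4.2 builds the End of Study PP set from ITT subjects without a Section 5.5 deviation "that could potentially affect the efficacy conclusions and at least 80% compliance with investigational product". Table 3 gives the same rule: "Subset of ITT Population with no major protocol deviation and at least 80% compliance with investigational product".

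**The concern.** The protocol singles out one kind of concomitant-medication change as able to alter the disease under study and bars it for everyone until Month 18. The SAP section that decides who leaves the PP set has no category for it. The result is also uneven. Inclusion criterion 3 requires subjects with a historical biopsy to be off these drugs, or on stable doses, for the 6 months before Day 1. A breach of it is an eligibility deviation and so excludes from PP. The same instability after Day 1, between the baseline and follow-up biopsies, does not, and no reason is given.

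Elsewhere the plan treats these drugs as important: baseline use is a randomization stratum, a stratum of the CMH test and an efficacy subgroup. At stake is whether a supportive PP result for histology means what Protocol 16.1 says it means.

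**Working it through.** There is no planned figure to reproduce, so the main check is a walk through the rules. Take a stage 2 or 3 subject who was eligible at entry, took the assigned product with at least 80% compliance, had no bariatric surgery, and started a TZD at Month 6.

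- Protocol 9.3: breached.
- Eligibility deviation (SAP 5.5): no. Inclusion criterion 3 looks back from Day 1 only.
- Product dosing deviation (SAP 5.5): no.
- Product after bariatric surgery (SAP 5.5): no.
- Compliance below 80% (SAP 3.4.2, Table 3): no.

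The subject stays in the End of Study PP set.

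Is that set used for histology at End of Study? This is an inference from three places. The Protocol synopsis, under efficacy analyses, plans supportive analyses in the PP population without limiting them to Month 18. SAP 3.4.2 defines a PP set specifically for End of Study. SAP 6.4.5, whose title covers both time points, says its analyses are also run in PP and then that "At the End of Study Analysis, all Month 18 histological endpoints will be analyzed". No sentence states it outright.

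Size. The documents give neither the number of breaches nor their effect on histology, so every rate below is an assumption.

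- Planned stage 2/3 subjects per arm: 2085 / 3 = 695, before any PP exclusion.
- Breach share f of 1% to 5%: 0.01 × 695 = 6.95 (about 7 subjects) to 0.05 × 695 = 34.75 (about 35).
- If breaching subjects' response rate differs from that of the others by g, the arm's PP rate moves by f × g. With g of 10 to 30 points: 0.01 × 10 = 0.1 up to 0.05 × 30 = 1.5 points.
- If f were 5% on OCA and 1% on placebo with the same g, the treatment difference would move by (0.05 − 0.01) × 10 = 0.4 to (0.05 − 0.01) × 30 = 1.2 points.
- For scale, with an assumed 20% response in both arms, the standard error of that difference is √(2 × 0.20 × 0.80 / 695) = 0.0215, about 2.1 points.
- Precision lost by excluding these subjects, 1/√(1 − f): 1.005 at 1% and 1.026 at 5%.

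End of the restricted period. Protocol 9.9.1 defines a month as 28 days, so Month 18 is 18 × 28 = 504 days. This agrees with Week 72 in SAP 4.3 (72 × 7 = 504).

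**The case against.** The strongest reply is that an 18-month rule fits the Month 18 biopsy better than End of Study. SAP 2.3.2.2.1 covers all post-baseline biopsies at End of Study, and these include Month 48. Subjects randomized on or after 16 July 2017 without a Month 18 biopsy no longer need one (Protocol 9.9.7). The fix would remove a subject with a short vitamin E dose change at Month 3 and keep one who starts a TZD at Month 19. This stands as a limit on what the fix achieves. It does not remove the gap: the Month 19 change is permitted and the Month 3 change is a breach, and a PP set is defined by breaches.

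Second, PP use at End of Study is only inferred. The PP sentence in SAP 6.4.5 also lists the mITT population, which Table 3 marks as not applicable at End of Study, so it may have been written for Month 18. This stands too, and is why the point is minor.

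Third, the list in SAP 5.5 may not be closed. It names two categories without calling them examples, so if more are intended they should be named. SAP 10.2 summarizes exposure to newly started vitamin E and TZDs, and SAP 4.4 plans efficacy subgroups, including in PP, by new antidiabetic medication. Both could reveal an imbalance, but neither affects PP membership. The text of SAP 6.2.3 and SAP Addendum V2.0 were not available, so the point concerns SAP 5.5 as written.

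Fourth, the exclusion would rest on a post-randomization event and be defined after a selected group was unblinded for the interim (SAP 2.2.4). That is true, but the End of Study PP set already excludes on compliance and already differs from the interim PP set.

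A reader might go further and infer that the protocol's own hyperglycemia guidance (Section 9.3.4 and Appendix B, whose figure legend expands TZD) makes these breaches likely, and likelier on OCA. The documents do not support that. Appendix F marks both as new in Version 11.0 of 4 May 2021. Subjects randomized by 15 July 2017 would have reached their Month 18 biopsy visit by December 2018 (SAP 3.4.1), and anyone randomized before about 17 December 2019 had passed Day 504 when the text appeared. The end of enrolment is not given, so later subjects cannot be ruled out. The figure itself is not shown, and a legend entry is not a recommendation.

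**Conclusion.** The gap is real and small. As written, SAP 5.5 lets subjects with the one concomitant-medication breach that the protocol prohibits as potentially NASH-modifying remain in the End of Study PP Population, unless they leave it for another reason. The consequence is confined to supportive PP results for histology at End of Study and depends on the inference that such results will be produced. It would be wrong to read this as a threat to the primary conclusions: the End of Study primary analysis names the ITT Population (SAP 6.4.4.2), and alpha, power and the already analysed interim PP set are untouched. The effect cannot be estimated from the documents. Under the assumptions shown it is 0.1 to 1.5 points in an arm and 0.4 to 1.2 points in the difference, less than one standard error of about 2.1 points. Nothing is claimed about how often breaches occurred, whether they differ by arm, or changes after Month 18.

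**What to change.** Before End of Study unblinding, add one sentence to SAP 5.5: for the End of Study PP Population and the histological endpoints, any start, stop or dose change of a TZD/glitazone or vitamin E from Day 1 to the Month 18 visit (Day 504 if that visit did not take place) is a major protocol deviation. Confine it to End of Study, because the interim PP definition in SAP 3.4.1 also refers to Section 5.5, and record the change in SAP Section 11. Report the count by arm, which follows from the existing rule on summarizing major deviations, and show PP histology with and without these subjects.

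The cost is one sentence, one note, one derived flag and a second display. Protocol 9.3 already requires concomitant medications and their dose changes to be recorded. SAP 10.2 already derives new use of vitamin E and TZDs; stops and dose changes need one further derivation from the same data. There are three downsides:

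- A slightly smaller PP set, with the standard error up by about 0.5% to 2.6% if 1% to 5% are excluded.
- Exclusion on a post-randomization event that may differ by arm, which the two-way display makes visible.
- No protection against the changes that the protocol permits after Month 18.

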9.3.1. Bile Acid Sequestrants

Bile acid sequestrants (BAS) have the potential to bind to fat-soluble vitamins, hormones, or medications. Subjects taking BAS (including colestyramine and its derivatives, colestipol, colesevelam, or other sequestrants) or aluminum hydroxide- or smectite-containing antacids should be instructed to stagger their dosing of investigational product in temporal relationship to these agents, ensuring at least 4 hours between doses of the BAS and/or these antacids and the investigational product (ie, BAS should be administered 4 hours before or 4 hours after investigational product administration). For guidance on using BAS to treat pruritus \leq Grade 2 in severity refer to [Section 15.1.5.1](#).

Due to the potential of BAS to affect the disposition of OCA, long-term use of BAS should be avoided where possible while taking investigational product. In subjects taking long-term BAS for other medical conditions (eg, hypercholesteremia), other therapies to replace the BAS should be considered.

9.3.2. Other Concomitant Medications

The effect of OCA on drug metabolizing enzymes has been evaluated in both in vitro and clinical studies. The PK profile of caffeine, a sensitive CYP1A2 substrate, showed weak effect of OCA on CYP1A2. Based on these results, OCA may increase the exposure of narrow therapeutic index drugs that are substrates for CYP1A2, such as theophylline and tizanidine.

If non-invasive indicators of progression to cirrhosis become evident at any time during the study, it is recommended that a liver biopsy should be obtained and sent for central reading (refer to [Section 7.4.2](#)).

[figure not shown]
If a study subject receives a COVID-19 vaccination, the date(s) of vaccination, vaccine name, and manufacturer should be recorded as a concomitant medication for each dose (refer to [Section 10](#)).

